10.6 Immunogenicity Assessments

Immunogenicity assessments to assess the immune response induced by vaccination with CVnCoV are only performed in a subset of Phase 2b subjects, the IS, and are evaluated in 2 ways:

- Binding antibodies to the SARS-CoV-2 RBD of the S protein Immunoglobulin G (IgG) measured in serum by immunoassay.

- Viral neutralizing antibodies directed against SARS-CoV-2 (MN 25 TCID50) measured in serum by a functional activity assay.

Results from the two assays are quantitative. Measures below the LLoQ are presented as half the LLoQ in the data.

Assessments for serology status to natural SARS-CoV-2 infection (SARS-CoV-2 N protein) are performed by immunoassay in all subjects. The N protein is not a component of the CVnCoV vaccine, but is measured to determine the serostatus of subjects to the SARS-CoV-2 virus and the occurrence of SARS-CoV-2 infections during the trial. Data provided is qualitative (positive/negative).

Additionally, CMI is evaluated in 200 (100 per treatment group) subjects in selected sites.

As some immunogenicity results could potentially unblind the subject's treatment assignment, the laboratory performing the concerned assays (IgG and MN 25 TCID50) keeps the results in strict confidence. The SARS-CoV-2 N protein data is not considered unblinding information.

10.6.1 SARS-CoV-2 Serology Status

For all subjects in the Phase 2b and Phase 3 parts of the trial, measurement of binding antibodies to the SARS-CoV-2 N protein are performed by immunoassay. Blood samples are taken on Day 1 (pre-vaccination baseline), Visit Day 43, Visit Day 211 and Visit Day 393 of the trial. (Day 393 assessments are only taken until the Urgent Safety Measure (USM) was implemented on 30-November-21.)

The (retrospective) SARS-CoV-2 serology status is defined based on levels of antibodies to the SARS-CoV-2 N protein. Subjects are defined as naïve to SARS-CoV-2 infection at baseline and Day 43, respectively, if there are no detectable SARS-CoV-2 N protein antibodies in the blood samples taken at baseline and Day 43, respectively.

Serology status at baseline is based on blood samples taken at Clinic Visit 1 (Visit Day 1) up to 2 days after 1st CVnCoV/placebo vaccination. The baseline definition for serology status is differing from the general baseline definition in this study (see Section 10.1).

Serology status at Visit Day 43 is based on blood samples taken at Clinic Visit 3 (Visit Day 43) 14 days after 2nd CVnCoV/placebo vaccination +/- 3 days.

For safety analyses, N antibody serostatus at baseline is used to define the seronegative and seropositive safety populations.

For the primary efficacy analyses, the subject must be seronegative/naïve to N protein at baseline and Visit Day 43 to be considered naïve when COVID-19 cases are being counted \geq 15 days after second trial vaccination. For endpoints where cases are counted at any time after the 1st trial vaccination, these subjects only have to be seronegative/naïve at baseline.

The same definition as given above is applied to assess the SARS-CoV-2 serology status of subjects at any other timepoint where a respective blood sample was taken; to measure infections with SARS-CoV-2 during the course of the trial.

Nota bene: Although the N antibody serostatus is to be considered an immunogenicity assessments, these values are not censored due to AV receipt.

10.6.2 Seroconversion

Seroconversion is defined by a relevant increase in antibody titer compared to baseline. The titer is the highest dilution factor that still yields a positive reading for the antibodies, i.e. larger titers correspond to larger concentration of antibodies. Depending on the type of antibodies and previous exposure of a subject to SARS-CoV-2 (as measured by antibodies to the SARS-CoV-2 N protein), different definitions of seroconversion apply:

10.6.2.1 SARS-CoV-2 RBD of S Protein Antibodies

In subjects who tested seronegative to the N protein for SARS-CoV-2 at baseline (see Section 10.6.1), seroconversion is defined as a fold increase above 1 in antibody titer against SARS-CoV-2 RBD of S protein.

In subjects who tested seropositive to the N protein for SARS-CoV-2 at baseline (see Section 10.6.1), the definition for seroconversion is a fold increase above 2 in antibody titer against SARS-CoV-2 RBD of S protein versus baseline.

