Seroconversion is defined as detectable SARS-CoV-2 RBD of S protein antibodies in the serum of subjects who tested seronegative at baseline.

SARS-CoV-2 viral neutralizing antibody responses

On Days 1, 29, 43, 120, and 211:

- Serum viral neutralizing antibodies to SARS-CoV-2 virus, as measured by a viral neutralizing antibody assay.
- Occurrence of seroconversion to SARS-CoV-2 virus, as measured by a viral neutralizing antibody assay.

Seroconversion is defined as detectable SARS-CoV-2 viral neutralizing antibodies in the serum of subjects who tested seronegative at baseline.

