10.3.6 Secondary and Exploratory Immunogenicity Analysis

No formal hypothesis on immunogenicity will be tested. Descriptive statistics for the immunogenicity endpoints will be provided for each vaccine group and overall, and by vaccine group and age groups. Data will be presented after each vaccine dose.

The following analyses will be performed for antibody levels to the SARS-CoV-2 RBD of S protein and for neutralizing antibodies overall and separately in subjects seronegative at baseline and in subjects seropositive at baseline:

- Geometric mean titers (GMTs) will be summarized with their 95% CI at each blood sampling time point.
- The Fold Change (FC) from baseline will be computed for each subject and Geometric mean of FC (GMFC) will be displayed with their 95% CI at each blood sampling time point after baseline.

Non-detectable antibodies will be arbitrary replaced by half of the detection cut-off for GMT and GMFC computations purpose.

For each readout, the number and percentage of subjects SARS-CoV-2 seronegative at baseline for whom a seroconversion is observed will be summarized and presented at each blood sampling time point after baseline with exact 95% CI. Seroconversion is defined as detectable antibodies in the serum.

Percentages of subjects seroconverting for SARS-CoV-2 RBD of S protein antibodies and SARS-CoV-2 neutralizing antibodies will be summarized. The frequency of immune cell populations induced by the vaccine will be summarized. Further characterization of the T-cell immune response may be done with other technologies like ELISpot, CyTOF and/or analysis of genomic biomarkers.

Additional immunogenicity analyses including graphs will be described in the SAP as applicable.

CV-NCOV-004
COVID-19 mRNA Vaccine

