9.2.3 Secondary Immunogenicity Endpoints (Phase 2b Immunogenicity Subset)

Scenario A: Exclude Day 57.

- SARS-CoV-2 RBD of the S protein antibody responses on Days 1, 29, 43, 57, 120 and 211:
 - Serum antibodies to SARS-CoV-2 RBD of the S protein, as measured by immunoassay.
 - Occurrence of seroconversion to SARS-CoV-2 RBD of S protein.

Thereby, seroconversion is defined as detectable SARS-CoV-2 RBD of S protein antibodies in the serum of subjects who tested seronegative at Day 1 (baseline), see Section 10.6.1 and Section 10.6.2.1 for details.

- SARS-CoV-2 viral neutralizing antibody responses on Days 1, 29, 43, 57, 120 and 211:

- Serum viral neutralizing antibodies to SARS-CoV-2 virus, as measured by a functional activity assay.
- Occurrence of seroconversion to SARS-CoV-2 virus.

Thereby, seroconversion is defined as detectable SARS-CoV-2 viral neutralizing antibodies in the serum of subjects who tested seronegative at Day 1 (baseline), see Section 10.6.1 and Section 10.6.2.2 for details.

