10.6.2.2 SARS-CoV-2 Neutralizing Antibodies

In subjects who tested seronegative to the N protein for SARS-CoV-2 at baseline (see Section 10.6.1), seroconversion is defined as a fold increase above 1 in SARS-CoV-2 neutralizing antibody titer.

In subjects who tested seropositive to the N protein for SARS-CoV-2 at baseline (see Section 10.6.1), the definition for seroconversion is a fold increase above 2 in SARS-CoV-2 neutralizing antibody titer versus baseline.

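### Seroconversion has two undeclared definitions (any fold rise above 1, and detectable), and neither identifies a response in N-seronegative subjects whose baseline titre is already quantifiable

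*SAP*

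**What the plan says.** The operational rules are in SAP 10.6.2. For N-seronegative subjects and RBD binding antibody, "seroconversion is defined as a fold increase above 1 in antibody titer against SARS-CoV-2 RBD of S protein"; for neutralizing antibody, "seroconversion is defined as a fold increase above 1 in SARS-CoV-2 neutralizing antibody titer". For N-seropositive subjects the bar is higher: "the definition for seroconversion is a fold increase above 2 in antibody titer against SARS-CoV-2 RBD of S protein versus baseline". The lead-in to these subsections sets a principle: "Seroconversion is defined by a relevant increase in antibody titer compared to baseline".

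The endpoint definitions read differently. SAP 9.2.3 states that "seroconversion is defined as detectable SARS-CoV-2 RBD of S protein antibodies in the serum of subjects who tested seronegative at Day 1" and refers the reader for details to the subsections that use fold above 1. SAP Table 1 (Section 9.5) repeats the detectable wording for both assays. Protocol 4.2.2 has "Seroconversion is defined as detectable SARS-CoV-2 RBD of S protein antibodies in the serum of subjects who tested seronegative at baseline", and Protocol 10.3.6 has "Seroconversion is defined as detectable antibodies in the serum". SAP 6.2, which lists intended departures from protocol version 4.0, does not mention seroconversion to RBD or neutralizing antibody.

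SAP 12.8.1 tabulates, at each post-baseline timepoint, the percentage seroconverting with any fold increase, with a 2-fold increase and with a 4-fold increase. It does so only in subjects who were N-seronegative at baseline.

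**The concern.** Baseline serostatus is set by N antibody alone (SAP 10.6.1). Nothing in SAP 12.8.1 requires the baseline RBD or neutralizing titre to be below the LLOQ. A subject who is N-negative but already has a quantifiable titre therefore enters the seroconversion denominator. The protocol contemplates such people: Section 9.2.1.1 treats seropositivity to S and/or N as evidence of prior infection, and Section 6 does not exclude laboratory evidence of prior infection.

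For such a subject a ratio of 1.01 satisfies SAP 10.6.2.1, although it is hardly a relevant increase. Two analysts working from different sections of the same SAP could report different rates for a named secondary endpoint. The any-fold column is the one that matches the SAP's operational definition, so a reader would take it as the endpoint result. The end-of-trial repeats in SAP 12.8.1, on the 228 primary-analysis subjects and 350 others, would inherit the same rule.

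**Working it through.** The documents give no expected seroconversion rate, power or assay precision, so there is no planned figure to reproduce. The check has three steps.

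**1. Do the rules agree?** SAP 10.3 sets values below LLOQ to 0.5 × LLOQ. Take LLOQ = 1 and let detectable mean at or above LLOQ (an assumption; Protocol 10.3.6 speaks of a detection cut-off).

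| Baseline | Post-baseline | Fold | Fold > 1 | Detectable |
|---|---|---|---|---|
| 0.5 (below LLOQ) | 0.5 (below LLOQ) | 1.0 | no | no |
| 0.5 (below LLOQ) | 1.0 | 2.0 | yes | yes |
| 2.0 | 2.02 | 1.01 | yes | yes |
| 2.0 | 1.5 | 0.75 | no | yes |
| 2.0 | 0.5 (below LLOQ) | 0.25 | no | no |

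With baseline below LLOQ the rules coincide. With a quantifiable baseline they do not. Fold above 1 counts any upward fluctuation; detectability counts everyone who stays at or above LLOQ.

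**2. How often is an unchanged subject counted?** Assume independent log-normal assay error of equal size at each visit, with σ = √ln(1 + CV²). Then P(fold > c) = 1 − Φ(ln c / (√2 σ)).

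- c = 1: ln 1 = 0, so the probability is 50% at any CV.
- c = 2, CV 20%: σ = 0.198 and ln 2 / (1.414 × 0.198) = 2.47, giving 0.7%.
- c = 2, CV 30%: σ = 0.294 and ln 2 / (1.414 × 0.294) = 1.67, giving 4.8%.

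The 50% needs a continuous readout. SAP 10.6.2 describes a titre as the highest dilution still positive, which is discrete and allows ties. The dilution step is not stated. Assuming 2-fold steps, simulation with 400,000 draws gives a chance rise of at least one step in 16% at CV 20% and 23% at CV 30% (31% at CV 50%). A rise of at least two steps, which is what above 2-fold requires on that scale, occurs in 0.1% and 1.2% at CV 20% and 30%.

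**3. Size in the placebo group.** The immunogenicity subset is 1,200 subjects at 1:1, so about 600 placebo subjects; the N-seronegative per-protocol number will be smaller. Let q be the share with a quantifiable baseline, assumed 0–5%. At q = 5% that is 30 of 600.

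- Fold > 1, continuous: 5% × 50% = 2.5 points (15 of 600).
- Fold > 1, 2-fold steps: 5% × 16% = 0.8 points at CV 20%; 5% × 22.7% = 1.1 points at CV 30%.
- Literal detectability: up to about 5 points (30 of 600).
- Rise above 2-fold, continuous: 5% × 0.7% = 0.03 points at CV 20%; 5% × 4.8% = 0.24 points at CV 30%.

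At q = 0 all of these are zero.

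**The case against.** The best defence is that fold above 1 is simply how the SAP implements detectability. Section 9.2.3 points to 10.6.2.1 and 10.6.2.2 for details, and for the expected subject, with baseline below LLOQ, step 1 shows that the two rules give the same answer. That stands.

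A reader might infer that the SAP rule inflates rates relative to the protocol. The documents do not support this: where the rules differ, fold above 1 counts fewer unchanged subjects than literal detectability. The weakness they share is the N-only entry criterion, so going back to detectable would not cure it.

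A reader might also chain the four analysed post-baseline visits (Days 29, 43, 120 and 211) and reach 80%, the chance that baseline is not the highest of five exchangeable values (4/5). SAP 12.8.1 reports by timepoint and has no ever-converted endpoint, so that figure describes nothing planned. Nor can one say that the true placebo rate is near zero, since placebo subjects can be infected during follow-up.

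The existence of affected subjects is possible but not shown. Protocol 6.2 excludes prior confirmed COVID-19, prior investigational SARS-CoV-2 vaccination and other coronavirus vaccines.

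Finally, the planned 2-fold column comes close to a sound rule. On a continuous readout, taken as at least 2-fold, it counts a move from below LLOQ to LLOQ or above and screens out most noise. On a 2-fold dilution scale, however, a one-step rise is exactly 2-fold, so that column would equal the any-fold column. It mitigates the problem but does not settle which rate is the endpoint.

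**Conclusion.** The inconsistency is real and undeclared, and its effect is small. It matters only for N-seronegative subjects with a quantifiable RBD or neutralizing baseline. For them neither rule identifies a response: without true change, fold above 1 counts about 50% per visit on a continuous readout or about 16–23% on an assumed 2-fold dilution readout at CV 20–30%, and detectability counts nearly all.

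Under fold above 1 the placebo rate would be overstated by about 0–2.5 points per visit. That range rests on an assumed share of 0–5%, which the documents neither give nor bound. Protocol 10.3.6 plans no formal immunogenicity test, so a reader should not infer any effect on type I error, power or the efficacy conclusions. This is a clarification worth making, not a threat to the trial.

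**What to change.** Use one definition for N-seronegative subjects, for both assays:

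- baseline below LLOQ: a post-baseline value at or above LLOQ;
- baseline quantifiable: a rise above 2-fold, the SAP's existing threshold for N-seropositive subjects.

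State it the same way in SAP 9.2.3, both immunogenicity rows of Table 1, 10.6.2.1, 10.6.2.2 and 12.8.1. Report that rate as the seroconversion endpoint and keep the any-fold rate as a descriptive line. Say whether the 2-fold column means at least 2-fold or more than 2-fold. Reporting the number of N-seronegative subjects with a quantifiable baseline, by group, would show whether the choice mattered.

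The programming cost is one condition in a derivation; no new data are needed. The procedural cost is larger. SAP 6.1 records that version 5.0 was written and approved by an unblinded team, and SAP 8.8 has the immunogenicity data merged once the trial was unblinded at the final primary analysis. List the change in SAP 6.2 as a departure from the protocol's detectable wording made after unblinding, with its reason.

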10.6.2.2 SARS-CoV-2 Neutralizing Antibodies

In subjects who tested seronegative to the N protein for SARS-CoV-2 at baseline (see Section 10.6.1), seroconversion is defined as a fold increase above 1 in SARS-CoV-2 neutralizing antibody titer.

In subjects who tested seropositive to the N protein for SARS-CoV-2 at baseline (see Section 10.6.1), the definition for seroconversion is a fold increase above 2 in SARS-CoV-2 neutralizing antibody titer versus baseline.

10.6.3 Cell-mediated Immunity

CMI is evaluated in approximately 200 subjects in selected sites.

The frequency and functionality of SARS-CoV-2 RBD of S-specific T-cell response after antigen stimulation is determined in PBMC in comparison to baseline. CMI assessment is performed on Day 1 (baseline), Day 29, Day 43, Day 120 and Day 211. Note that testing on Day 120 and Day 211 is only performed on subjects who are determined as T-cell responders on Day 29 and/or Day 43.

10.7 COVID-19 Cases

COVID-19 case ascertainment occurs in an identical manner in both the Phase 2b and Phase 3 parts of the trial. Case detection begins with the identification of subjects reporting at least one symptom from a standardized list of symptoms. Based on a scripted phone interview with trial staff, subjects suspected of having COVID-19 undergo testing for SARS-CoV-2 virus. Details of the tests performed and, in case of confirmed COVID-19 cases, details on the COVID-19 cases are recorded on the CRF.

Scenario A: For consistency reasons, although the efficacy analysis has already been completed, the reporting procedure for COVID 19 cases in the open-label phase remains the same as in the randomized observer blinded phase (however, a reduced list of symptoms is used).

10.7.1 Case Detection

10.7.1.1 Routine Surveillance

During all clinic visits and phone calls, subjects are reminded to contact the trial site if they have any of the following symptoms [4]:

- **Fever** or Chills
- **Shortness of breath** or difficulty breathing
- **New loss of smell or taste**
- **Cough**
- Fatigue
- Muscle or body aches
- Headache
- Sore throat
- Congestion or runny nose

- Nausea or vomiting
- Diarrhea

Scenario A: Only symptoms in bold underline are effective.

In addition, subjects are messaged up to twice a week to provide a yes or no response to having COVID-19 symptoms.

Scenario A: Mobile Health Platform (MHP) is switched off, only passive surveillance is performed (subject to call site in case of symptoms).

Those who report symptoms either at the clinic visit or by phone call, or respond “yes” to having symptoms by messaging are contacted by trial staff for a follow-up interview(s) to determine the probability of the subject having COVID-19. If the subject is suspected of having COVID-19 illness, he/she undergoes testing for SARS-CoV-2 infection, consisting of a rapid antigen test performed locally by the trial staff and a molecular-based RT-PCR test performed at a designated central laboratory.

The result of both the antigen test and the central RT-PCR test are recorded on the CRF as positive or negative.

10.7.1.2 Non-Routine Surveillance for COVID-19 (Positive Test Outside of Trial Site)

Subjects are reminded to contact the trial site immediately if he/she has a positive SARS-CoV-2 test performed outside of the trial site, and they were symptomatic (COVID-19 illness) or asymptomatic at the time of the test.

The subject should be retested as soon as feasible to have the result confirmed by the central laboratory. This RT-PCR test result is considered definitive as a virologically-confirmed case of COVID-19. If the subject is not virologically-confirmed by RT-PCR testing, he/she returns to routine surveillance for COVID-19 as a subject who is naïve to SARS-CoV-2 infection (unless determined otherwise by a seropositive test to the N protein).

If the subject was symptomatic, trial staff use the scripted interview to collect information about the subject's COVID-19 symptoms and medical condition.

Scenario A: No RT-PCR confirmation of positive test results that were performed outside the trial site is to be performed. Neither on suspected symptomatic or on suspected asymptomatic infections.

10.7.2 Definition of Virologically-Confirmed COVID-19 Case and Onset Date

A virologically-confirmed case of COVID-19 is defined as a positive SARS-CoV-2 specific RT-PCR test performed at a designated central laboratory in a person with clinically symptomatic disease consisting of one or more of the symptoms listed in Section 10.7.1. The onset date of a virologically confirmed COVID-19 case (identified during routine surveillance or outside of the trial) is defined as the date of symptom onset as recorded on the CRF. If the date of symptom onset is partially or completely missing, the following imputation rules are applied:

1. If the date is present but incomplete and it can be confirmed, based on the available date parts, that the onset was before first vaccination, then the missing date parts are imputed as the earliest possible date.
2. If a present but incomplete date is still incomplete after checking point 1, and it can be confirmed, based on the available date parts, that the onset was before 15 days after second vaccination, the missing date parts are imputed with the earliest possible date on or after first vaccination.
3. If a present but incomplete date is still incomplete after checking points 1 and 2, it is imputed with the earliest possible date \geq 15 days after second vaccination.
4. If the symptom onset date is completely missing, the date of first positive RT-PCR test is used instead.

a) If the first positive RT-PCR test is incomplete then points 1-3 above should be applied on the first positive RT-PCR test date.

10.7.3 Definition of Mild, Moderate and Severe COVID-19 Cases

Mild COVID-19 cases are defined as virologically (RT-PCR) confirmed cases fulfilling all of the following:

- Symptomatic,
- No shortness of breath or difficulty breathing,
- No hypoxemia, i.e. oxygen saturations in arterial blood (SpO₂) saturation \geq 95% on room air at sea level; SpO₂ should be adjusted according to altitude.
- Does not meet the case definition of moderate or severe COVID-19.

Moderate COVID-19 cases are defined as virologically (RT-PCR) confirmed cases fulfilling any of the following criteria:

- Shortness of breath or difficulty breathing
- Respiratory rate \geq 20 to < 30 breaths per minute
- Abnormal SpO₂, but still $>$ 93% on room air at sea level; SpO₂ should be adjusted according to altitude.
- Clinical or radiographic evidence of lower respiratory tract disease
- Radiologic evidence of deep vein thrombosis (DVT)

Severe COVID-19 cases are defined as virologically (RT-PCR) confirmed cases fulfilling any of the following:

- Clinical signs at rest indicative of severe systemic illness (respiratory rate \geq 30 per minute, heart rate \geq 125 per minute, SpO₂ \leq 93% on room air at sea level or arterial oxygen partial pressure/fractional inspired oxygen [PaO₂/FIO₂] $<$ 300 mmHg). SpO₂ should be adjusted according to altitude.
- Respiratory failure (defined as needing high flow-oxygen, noninvasive ventilation, mechanical ventilation or Extracorporeal membrane oxygenation [ECMO])
- Evidence of shock (systolic blood pressure [SBP] $<$ 90 mmHg, diastolic blood pressure [DBP] $<$ 60 mmHg, or requiring vasopressors)
- Significant renal, hepatic, or neurologic dysfunction
- Admission to Intensive Care Unit (ICU)
- Death

A fourth category of “moderate to severe” cases is further defined, combining cases of moderate severity and cases of severe severity.

